## **9. RESEARCH METHODS**

### **9.1. Study design**

This is a non-interventional, retrospective cohort study using secondary data sources containing structured data from the US. This study will include adults (≥18 years of age) and pediatric participants (<18 years of age) with a positive SARS-CoV-2 test (e.g., positive polymerase chain reaction (PCR) of direct SARS-CoV-2 viral testing).

### **9.2. Setting**

This study will be conducted using SARS-CoV-2 diagnostic testing data from the Helix Respiratory Registry with linkage to the Komodo Healthcare claims data during the period of 01 June 2020, to 28 February 2023. Details about the database are found in Section 9.7. Further details will be outlined in the Statistical Analysis Plan (SAP).

### **9.2.1. Study population and cohorts**

The study population will be generated from the two US databases described in Section 9.2.

The main cohort will include all participants meeting inclusion and exclusion criteria outlined in Section 9.3.

The high-risk subcohort (if sample size is limited, age (<50 years of age versus 50+ years of age) will be used as a proxy for high-risk for progression to severe SARS-CoV-2 status) will include all participants in the main cohort with high-risk clinical characteristics (comorbidities) for progression to severe SARS-CoV-2, as outlined in Section 9.4.

### **9.2.2. Time periods**

#### **9.2.2.1. Study period**

The study will include an overall study period of June 01, 2020, to February 28, 2023.

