### **Primary Objectives:**

**Objective 1:** To estimate viral SARS-CoV-2 rebound rates (primary definition: 1. a positive test (at the index date), followed by a single negative test, followed by a positive test - within 28 days, or 2. 1 or more positive tests at the index date, followed by 1 or more negative tests, followed by a positive test within same 28 day time span), prior to the Omicron era and during the Omicron era (defined as 01 December 2021 to present), in high frequency (volume) SARS-CoV-2 diagnostic testers (primary definition: 1 or more positive tests followed by 1 or more negative tests followed by 1 or more positives within same 28 day time span and median time between tests (positive or negative) is at most 10 days).

**Objective 2:** To estimate viral SARS-CoV-2 rebound rates (using the primary definition of viral SARS-CoV-2 rebound), prior to the Omicron era and during the Omicron era, in high frequency (volume) SARS-CoV-2 diagnostic testers (using the primary definition of high frequency testing), among those treated with Paxlovid/nirmatrelvir-ritonavir for SARS-CoV-2 versus those with no evidence of SARS-CoV-2 treatment (untreated for SARS-CoV-2), stratified by:

- a. Demographics of participants
- b. Time from first positive test to treatment (if treated).
- c. Participants at high-risk for progression to severe SARS-CoV-2 versus those not at high-risk, if sample size allows. If sample size is limited, age (<50 years of age versus 50+ years of age) will be used as a proxy for high-risk for progression to severe SARS-CoV-2 status)

- d. Co-infections
- e. Vaccinated against SARS-CoV-2 (has received at least 1 dose) and time since last vaccine dose > 6 months vs. ≤6 months
- f. Multiple SARS-CoV-2 treatment prescription status

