#### **9.2.2.3. Index date**

Index date is defined as first confirmed positive SARS-CoV-2 rRT-PCR test within a positive - negative – positive test sequence that occurs within 28 days during the study period (by omicron era status). Only the first infection for each patient during the study period (by omicron era status) will be examined.

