## Endpoints

The following are the primary endpoint:

- Viral SARS-CoV-2 rebound\*, where the main definition defines rebound as 1.) a positive test (at the index date), followed by a single negative test, followed by a positive test - within 28 days, or 2.) 1 or more positive tests starting at the index date, followed by 1 or more negative tests, followed by a positive test within same 28-day time span. Index date will be defined as first positive test date.

The following are the exploratory endpoints:

- Clinical outcomes (within 30 days of index date), based on healthcare utilization following viral SARS-CoV-2 rebound
  - Hospitalization (including length of stay)
  - Hospitalizations with invasive mechanical ventilation
  - Emergency room visits
  - Urgent care visits
  - All-cause mortality

\*Alternate definitions of viral SARS-CoV-2 rebound will be included in sensitivity analyses and detailed in the SAP.

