## 9.6. Study size

This is a descriptive study with no minimum sample size. All eligible participants during the relevant study periods will be included. This is a NI study with no a priori hypotheses specified; therefore, sample size calculations are not applicable.

Preliminary feasibility counts provided to Pfizer, Inc. by Helix indicate that 1,244,791 SARS-CoV-2 diagnostic tests performed from 10 October 2020, to 10 August 2022, among individuals who have tested with a Helix SARS-CoV-2 diagnostic test through a retail pharmacy in the US, 558,340 of these tests were positive. These positive tests represent 449,759 unique infections, defined as positive tests more than 28 days apart. Among high frequency (volume) SARS-CoV-2 diagnostic testers (under the primary definition), there were 21,991 unique infections during the same time period.

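### One infection spanning 1 December 2021 can be counted in both eras, and no last index date leaves room for the 28- and 30-day outcome windows

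*Supplement*

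**What the plan says.** Section 9.2.2.1 fixes the calendar: "The study will include an overall study period of June 01, 2020, to February 28, 2023". Section 9.2.2.4 ends follow-up at the close of that period, or earlier at death, disenrollment or the outcome. Primary Objective 1 in Section 8 places the era boundary: "during the Omicron era (defined as 01 December 2021 to present".

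Section 9.2.2.3 takes the index from a positive-negative-positive "test sequence that occurs within 28 days during the study period (by omicron era status". It then limits each person to one infection per era: "Only the first infection for each patient during the study period (by omicron era status) will be examined". It requires no infection-free interval, and Section 9.3.2 lists no exclusions. A rule that separates infections appears only with the feasibility counts in Section 9.6, where unique infections are "defined as positive tests more than 28 days apart".

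The Endpoints part of Section 9.4 words the index differently: "Index date will be defined as first positive test date". It gives rebound a 28-day window ("followed by 1 or more negative tests, followed by a positive test within same 28-day time span") and the exploratory outcomes a 30-day one: "Clinical outcomes (within 30 days of index date". No section states a last eligible index date.

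**The concern.** Two edges of the calendar are left open.

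At the era boundary, choosing the first infection afresh in each era lets the tail of a November 2021 infection become the first Omicron-era infection of the same person. The harm goes beyond a duplicate count. The Omicron-era record would start from a positive test that is not the infection's first. That shifts the time from first positive test to treatment (Primary Objective 2b) and the week of initial positive test used in the weighted Cox model of Section 9.8. The same infection could also be coded as a prior SARS-CoV-2 infection among the covariates.

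At the end of the study, a late index date has fewer than 28 or 30 days in which the outcome can be seen. Section 9.8 describes categorical variables by numbers and percentages and mentions no allowance for censoring. If the rebound rates are reported that way, the shortfall falls on the Omicron era alone, and the two eras are no longer measured alike.

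**Working it through.** The plan gives no expected rate or sample size for this point, so there is no figure to reproduce. The check is date arithmetic on the written rules, plus a range for the size.

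**Inputs from the protocol**
- Study period, 1 June 2020 to 28 February 2023 (9.2.2.1): 1,003 days.
- Era boundary, 1 December 2021 (Section 8): 548 days before it and 455 from it to the study end.
- Outcome windows: 28 days for rebound and 30 days for clinical outcomes (9.4, Endpoints).
- Entry: at least three tests within 28 days of index, median gap at most 10 days (9.3.1).

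**Assumptions, not in the protocol**
- Omicron-era index dates are evenly spread.
- Time to viral rebound follows one of the four shapes below. The 9-day median in Section 7 refers to symptom rebound in treated patients and only shapes one curve.

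**Step 1: era boundary.** Take positive 20 November, negative 27 November, positive 4 December, negative 9 December, positive 14 December 2021. These fall on days 0, 7, 14, 19 and 24. The gaps are 7, 7, 5 and 5 days, median 6.
- Indexed 20 November (pre-Omicron): the sequence completes on day 14. There are five tests within 28 days and the median gap is 6. Eligible, rebound.
- Indexed 4 December (Omicron): the sequence completes 10 days later. There are three tests, with gaps 5 and 5. Eligible, rebound.
- Under 9.6, the first and last positives are 24 days apart, so this is one infection.

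With era read from the index date, one infection gives a rebound in each era. Under the Endpoints wording, 4 December is likewise the first positive test of the Omicron era. Index dates whose 28-day window crosses the boundary run from 3 to 30 November 2021: 28/548 = 5.1% of pre-Omicron days.

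**Step 2: end of study.**
- 28 February 2023 − 28 days = 31 January 2023, the last index date with a full rebound window.
- 28 February 2023 − 30 days = 29 January 2023, the last with a full clinical-outcome window.
- Omicron-era days without a full window: 28/455 = 6.2% for rebound and 30/455 = 6.6% for clinical outcomes.
- Secondary Objective 3 needs two positives more than 14 days apart. For an index on 14 February the earliest such day is 1 March, so no index from 14 February onward can meet it.

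**Step 3: size under the first-positive index.** Relative loss = f × (1 − mean F(d)). Here f = 28/455, d = 0 to 27 is the number of days left, and F is the distribution of time to rebound within 28 days.

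| Assumed time to rebound | Mean F(d) | Relative loss |
|---|---|---|
| Gamma (shape 4), median 9 days | 0.635 | 0.0615 × 0.365 = 2.2% |
| Gamma (shape 6), median 14 days | 0.472 | 0.0615 × 0.528 = 3.2% |
| Uniform, 0 to 28 days | 0.482 | 0.0615 × 0.518 = 3.2% |
| Uniform, days 3 to 28 | 0.446 | 0.0615 × 0.554 = 3.4% |

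If the share of late index dates were 1% to 15% instead, the loss would run from 0.01 × 0.365 = 0.4% to 0.15 × 0.554 = 8%.

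**Step 4: size under the sequence-based index.** If the index needs a completed positive-negative-positive sequence, everyone included has already rebounded. An incomplete late sequence then leaves numerator and denominator together, and truncation does not lower the rate.

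**The case against.** The strongest reply is that the protocol closes both gaps by implication and leaves the rest to an SAP that is not shown. Section 9.2.2.3 speaks of the first infection, and the only definition of an infection, in 9.6, makes the example a single one. If era status applied to the whole sequence, the 20 November sequence would not complete before Omicron and only one era would count it. Section 9.2.2.4 defers follow-up details to the SAP, and the Cox model can censor at study end.

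Part of this stands. The SAP may settle follow-up, and the Cox comparison is less exposed than the percentages. But 9.6 is not tied to the index rule, and nothing says which era owns an infection that spans both. Reading era status as covering the whole sequence would truncate index dates from 3 November 2021 instead, and an infection with a complete sequence on each side of the boundary would still count twice. The double count follows from rules this protocol writes itself, not from detail it leaves out.

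Two stronger readings are tempting, and the documents do not support them:
- A reader might infer that index dates are accepted up to the last study day. Section 9.2.2.1 states only the study period. Section 9.2.2.3 needs the sequence inside it and 9.3.1 needs three tests, so an index on 28 February 2023 does not qualify in practice.
- A reader might infer a bias in the Paxlovid rates, because authorisation came in December 2021. Treated and untreated Omicron-era patients meet the same cut-off, and no calendar timing by treatment is given.

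The 15 March 2023 end of data collection adds nothing either way. Sections 9.2 and 9.5 stop the data at 28 February. Even data to 15 March would complete 28-day windows only for index dates to 15 February.

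**Conclusion.** The point holds in limited form. As written, the rules allow one infection spanning 1 December 2021 to count as a rebound in both eras. The documents give no count of such patients, so the frequency is unknown.

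The missing last index date is a smaller matter. It understates crude Omicron-era percentages only under the first-positive index of the Endpoints text. The loss is then at most about 2–3% in relative terms (2.2% to 3.4% across the shapes tried) if index dates are evenly spread. The three-test rule reduces it further, because many late index dates never enter the denominator. What is shown is a distortion between eras, in a descriptive study without hypotheses.

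That the two index definitions disagree is the larger issue behind this one, since under 9.2.2.3 the rebound rate is 100% by construction.

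**What to change.** 1. In 9.2.2.3, require no positive test in the 28 days before the index date, and assign each infection to the era of its first positive test. This carries the 9.6 rule into the analysis, so each infection is counted once.
2. Set the last eligible index date at 31 January 2023 for rebound and 29 January 2023 for the 30-day outcomes. Alternatively, keep later index dates and estimate rebound by a cumulative incidence that accounts for censoring.
3. Reconcile the index definition in 9.2.2.3 (repeated in 9.3.1 and at the start of 9.4) with the one under Endpoints, and repeat the result in the abstract and the SAP.

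The data are retrospective, so this costs a few lines of text and no new collection. The cut-off drops 6.2% (28 days) to 6.6% (30 days) of Omicron-era index days; the cumulative-incidence route avoids that loss.

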#### **9.2.2.2. Baseline period**

The 365 days before index date will be the baseline period.

#### **9.2.2.3. Index date**

Index date is defined as first confirmed positive SARS-CoV-2 rRT-PCR test within a positive - negative – positive test sequence that occurs within 28 days during the study period (by omicron era status). Only the first infection for each patient during the study period (by omicron era status) will be examined.

#### **9.2.2.4. Follow-up**

The follow-up period starts at index date and participants will be followed until the date of the first occurring of the following events:

- Death
- At the end of their database disenrollment from the database
- At the end of study period
- Occurrence of the outcome/endpoint of interest

Further details will be defined in SAP.

### 9.3.2. Exclusion Criteria

Participants in all cohorts are excluded from the study if the following criterion applies:

1. None / NA

## 9.4. Variables

All study variables of interest, including demographics, diagnostic (testing and disease), therapeutic and outcomes/endpoints are listed below. Index date is defined as first confirmed positive SARS-CoV-2 rRT-PCR test within a positive - negative – positive test sequence that occurs within 28 days. Baseline period will vary by patient, based on how much history is available and index date.

## Endpoints

The following are the primary endpoint:

- Viral SARS-CoV-2 rebound\*, where the main definition defines rebound as 1.) a positive test (at the index date), followed by a single negative test, followed by a positive test - within 28 days, or 2.) 1 or more positive tests starting at the index date, followed by 1 or more negative tests, followed by a positive test within same 28-day time span. Index date will be defined as first positive test date.

The following are the exploratory endpoints:

- Clinical outcomes (within 30 days of index date), based on healthcare utilization following viral SARS-CoV-2 rebound
  - Hospitalization (including length of stay)
  - Hospitalizations with invasive mechanical ventilation
  - Emergency room visits
  - Urgent care visits
  - All-cause mortality

\*Alternate definitions of viral SARS-CoV-2 rebound will be included in sensitivity analyses and detailed in the SAP.

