## 7. RATIONALE AND BACKGROUND

Coronavirus disease 2019 (COVID-19), caused by severe acute respiratory syndrome coronavirus 2 (SARS-CoV-2), was declared a global pandemic by the World Health Organization (WHO) on 11 March 2020^6, and continues to be a serious global threat to public health and to health care systems. As of 07 March 2022, COVID-19 has infected at least 446 million people, and has led to at least 6 million deaths worldwide.

In order to prevent SARS-CoV-2 infection, several COVID-19 vaccines have been approved or authorized for emergency use by Health Authorities and are being administered globally.

In December 2021, the Food and Drug Administration (FDA) granted emergency use authorization (EUA) for a 5 day course of treatment for 2 separate oral antiviral agents, nirmatrelvir/ritonavir and molnupiravir, for the treatment of COVID-19 in adult and pediatric patients 12 years of age and older who weigh at least 40 kg, with mild to moderate COVID-19 who are at high risk for progressing to severe illness. In January 2022, remdesivir received approval for this same population. This treatment is administered by IV infusion over 3 days for nonhospitalized patients with mild to moderate COVID-19 who are at high risk for progressing to severe illness.

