Case reports in the literature describe individuals who have experienced symptomatic relapses of SARS-CoV-2 infection following completion of a 5-day course of nirmatrelvir/ritonavir. In the available cases, patients are described as experiencing rapid improvement in systemic symptoms following initiation of treatment but then experience a rebound in COVID-19 symptoms after completing therapy. The time course of symptom rebound suggests that symptom recurrence is likely not related to re-exposure and that it does not reflect a potential re-infection event. In one case report, symptom relapse was accompanied by fluctuating reverse transcription polymerase chain reaction (RT-PCR) cycle thresholds and antigen testing suggesting the potential for a rebound in viral replication. In a separate case series of 7 patients with recurrent symptoms, median SARS-CoV-2 RNA at baseline was 6.1 log10 copies/mL (range 4.2-7.3) and enrollment viral cultures were positive in 3 of 7 individuals. Several of the published case reports on symptom recurrence included viral sequencing and these reports to date have not identified resistance mutations to nirmatrelvir.

A retrospective review of 483 high-risk patients treated with nirmatrelvir/ritonavir reported 4 (0.8%) of patients experienced rebound of symptoms. Median time to rebound was reported as 9 days.

Rebound symptoms were characterized as mild and resolving without additional COVID-19 therapy with no patient requiring hospitalization.

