## Covariates

Covariates will include baseline demographic, high-risk clinical characteristics (comorbidities) for progression to severe SARS-CoV-2, medications, and health utilization, as well as those needed for the study cohort inclusion and exclusion criteria. These are not intended to be the exclusive lists. Adjustments of the covariates may be made, and additional variables may be added in SAP as needed over time. The code lists of conditions and medications (if applicable) will be provided in SAP.

*Demographics (prior to index date):*

- Age/Age group (age groups to be defined in the SAP)
- Gender
- Race/ethnicity (if available)
- Location/region (if available)

*High-risk clinical characteristics (comorbidities) for progression to severe SARS-CoV-2 (prior to index date):*

- Immunosuppressive disease or immunosuppressive treatment.
- Cancer (active) other than localized skin cancer
- Cardiovascular conditions (Cerebrovascular disease or stroke, coronary heart disease, cardiomyopathies, heart failure, etc.)
- Chronic kidney disease (CKD)
- Deyo-Charlson Comorbidity Index Score
- Diabetes mellitus
- HIV
- Hypertension

- Chronic liver disease (cirrhosis; non-alcoholic fatty liver disease; alcoholic liver disease; autoimmune hepatitis, etc.)
- Neurodevelopmental disorders
- Obesity
- Respiratory conditions (Asthma, Chronic obstructive pulmonary disease (COPD), Interstitial lung disease (ILD), Chronic lung disease, etc.)
- Sickle cell disease
- Smoking status (current or former)

*Prior healthcare characteristics (prior to index date):*

- Prior-year healthcare utilization
- Prior SARS-CoV-2 infection/s
- Prior SARS-CoV-2 vaccination/s (never vaccinated,  $\geq 1$  dose with most recent dose given within 6 months of index date,  $\geq 1$  dose with most recent dose  $>6$  months from index date)
- Prior influenza vaccinations

*Risk factors to be examined (prior to index date):*

- All demographics, high-risk clinical characteristics (comorbidities) for progression to severe SARS-CoV-2 and prior healthcare characteristics mentioned above

*Diagnostic Testing Characteristics (on or after index date):*

- High frequency (volume) SARS-CoV-2 diagnostic testing status\*\*

*Medications for treatment of COVID-19 (on or after index date):*

- Anti-SARS-CoV-2 Monoclonal Antibodies
  - Bamlanivimab/Etesevimab
  - Casirivimab/Imdevimab
  - Sotrovimab
  - Tixagevimab/Cilgavimab
  - Bebtelovimab
- Antiviral therapy
  - Paxlovid/nirmatrelvir-ritonavir

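### The rebound endpoint takes no account of when treatment was given, so the Paxlovid rate in Primary Objective 2 mixes sequences completed before, during and after the 5-day course

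*Supplement*

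**What the plan says.** Protocol section 9.4 (Endpoints) defines rebound by the order and span of tests alone: "1 or more positive tests starting at the index date, followed by 1 or more negative tests, followed by a positive test within same 28-day" span. The anchor is explicit: "Index date will be defined as first positive test date". Section 9.2.2.4 uses the same origin for everyone: "The follow-up period starts at index date".

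Exposure is listed in section 9.4 (Covariates) under "Medications for treatment of COVID-19 (on or after index date"). It has no upper time limit and no required order relative to the negative test or the second positive.

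Section 7 describes a different event. The case reports concern patients who improve on treatment and "then experience a rebound in COVID-19 symptoms after completing therapy". The EPIC-HR figures quoted there are post-treatment increases measured relative to end of treatment. Section 7 also gives the course length, through the agency that "granted emergency use authorization (EUA) for a 5 day course of treatment for 2 separate oral antiviral agents".

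Primary Objective 2 (section 8) compares Paxlovid-treated with untreated patients and stratifies by "b. Time from first positive test to treatment (if treated"). Section 9.8 adds a Cox comparison with inverse probability of treatment weighting.

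**The concern.** The event that motivates the study happens after a course of treatment. The event that is counted can happen at any point in the 28 days after the first positive.

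Take a patient who fills Paxlovid on the day of the first positive (day 0), is negative on day 2 and positive on day 4. The median gap between tests is 2 days, so the high-frequency rule in section 9.3.1 is met. The endpoint is met as well. The patient is a Paxlovid rebound while still within the 5-day course. Treatment began on day 0, so no pre-treatment time is misassigned, and handling treatment as time-varying would not remove this case.

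Now take a patient who goes positive, negative, positive by day 8 and fills on day 10. As written, that sequence also counts in the treated group, although it was complete before any drug was dispensed.

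At stake is the meaning of the treated rate, of its contrast with the untreated, and of stratum b, where the split between these kinds of event changes with the stratifying variable itself.

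**Working it through.** The protocol states no sample size, power or expected rebound rate for this study, so there is no figure to reproduce. The check is day counting.

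**Inputs**
- Window: second positive by day 28, with the first positive on day 0 (section 9.4).
- Course length: 5 days (section 7).
- Treatment day k: assumed to be 0, 5 or 10. The documents give neither a distribution of treatment delay nor cut-points for stratum b.
- Weighting: every pair (day of negative, later day of second positive) within days 1 to 28 has equal weight. This illustrates the structure; it does not estimate real test timing.

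**Formulas**, with C(m,2) = m(m − 1)/2
- Course days: k to k + 4.
- Post-course days left in the window: 28 − (k + 4) = 24 − k.
- All pairs: C(28,2) = 378.
- Second positive before treatment: C(k − 1,2), or 0 when k = 0.
- Second positive on course: C(k + 4,2) minus the pairs completed before treatment.
- Negative and second positive both after the course: C(24 − k,2).
- Remainder: negative by the end of the course, second positive after it.

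**Results**

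| k | Post-course days | Second positive before treatment | Second positive on course | Negative by end of course, positive after | Both after |
|---|---|---|---|---|---|
| 0 | 24 | 0 (0.0%) | 6 (1.6%) | 96 (25.4%) | 276 (73.0%) |
| 5 | 19 | 6 (1.6%) | 30 (7.9%) | 171 (45.2%) | 171 (45.2%) |
| 10 | 14 | 36 (9.5%) | 55 (14.6%) | 196 (51.9%) | 91 (24.1%) |

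Pairs completed before the end of the course, all counted as Paxlovid rebound, are 6/378 = 1.6% at k = 0, 36/378 = 9.5% at k = 5 and 91/378 = 24.1% at k = 10.

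**With exactly three tests.** The median of two gaps is half the total span, so a median of at most 10 days puts the second positive by day 20. Post-course days are then 20 − (k + 4) = 16, 11 and 6.

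**The case against.** **A common index-anchored window is fair.** Every patient, treated or not, is observed over the same 28 days, and a sequence counts wherever it falls. This is a reasonable choice for a descriptive study, and it stands for Objective 1.

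It also disposes of a stronger reading. A reader might infer that later treatment must look protective because fewer post-course days remain. With a flat daily chance, and only post-course events counted, the shortfall against day 0 would be 5/24 = 21% at k = 5 and 10/24 = 42% at k = 10. The endpoint as written does not count only post-course events. Under the same flat chance applied to what is counted, the loss is zero, and the pre-treatment sequences that still count increase with k. Nor do the documents support a flat chance: section 7 reports a median of 9 days to symptom rebound and detection on Day 10 or Day 14.

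**The on-course share is small for prompt treatment.** Also correct. It is tempting to say that 5 of 28 days, or 18%, of the window is on treatment at k = 0. That is a share of days, not events. A second positive needs a negative before it, and the pair count gives 1.6%.

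**The plan partly handles this.** Section 7 promises to look at rebound timing in relation to treatment, but gives no rule that alters the endpoint. The alternate definition in Secondary Objective 3, two positives more than 14 days apart, excludes an on-course second positive when treatment starts by day 10. It is a sensitivity analysis, is not tied to treatment, and does not equalise post-treatment time. The SAP is not among the documents and may add detail. The primary definition is nevertheless fixed in the protocol, and section 9.8 says that major changes to it would be reflected in an amendment.

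**A more basic problem comes first.** Section 9.2.2.3 defines the index date as the first positive within a positive-negative-positive sequence. Read literally, everyone enrolled has rebounded. That is a separate defect. The present point assumes it is resolved, and resolving it would not settle where a sequence falls relative to the course.

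**Conclusion.** The point holds in a limited form. The treated rebound rate in Primary Objective 2, stratum b and the weighted Cox comparison combine sequences completed before, during and after the course, and the proportions depend on treatment day. None of the three can be read as the post-treatment rebound that section 7 describes.

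No direction or size of bias in the counted rate can be claimed. The percentages rest on equal weighting of day pairs and on assumed treatment days of 0, 5 and 10. The real effect depends on how soon patients filled and how often they tested, which the documents do not report. If nearly all fills were on or close to day 0, on-course completion would be a minor component. If a material share came later, stratum b in particular would be hard to interpret.

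**What to change.** Keep the index-anchored 28-day definition for Objective 1. For Objective 2, stratum b and the weighted comparison, add a treatment-anchored analysis:

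1. Class each sequence as completed before, during or after the course, using the fill date plus the protocol's stated 5 days. Do not attribute sequences completed before the fill to Paxlovid. Tabulate the classes by treatment day, and show separately those whose negative test fell on course.
2. Count as post-treatment rebound only a second positive after the course and within one pre-specified number of days from the fill, the same for all treated patients. State whether tests beyond day 28 from the first positive are used, since late fills would otherwise be cut short again.
3. In untreated patients who have not rebounded by that date, apply the same offset and length from a start date matched to the treated patients' fill dates.

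The cost is wording and re-coding from test and fill dates that the linked data already hold. Fewer events will be counted in the treated-versus-untreated analysis, and the fill date is only a proxy for the first dose. If this replaces the primary definition for Objective 2 and does not merely sit beside it, section 9.8 calls for a protocol amendment.
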